### 8.4.2 Study Procedures

# Screening assessments (Day -28 to Day -8)

Subjects will be screened for enrolment within 3 weeks prior to the start of baseline assessments. Subjects will be screened in accordance with predefined entrance criteria as described in Sections 8.1 and 8.2. See Section 8.5.1 for the procedure for documenting screen failures.

Procedures to be completed at screening include:

- Subject information/Informed consent signed and dated.
- Assessment of inclusion / exclusion criteria.
- Demographics
- Medical history and previous medication (prohibited as of 4 weeks before D-28)
- Concurrent medical condition
- Physical examination
- Vital signs

Amendment 04, Final Version 1.0
Protocol No.: BB-2001-201b
EudraCT No.: 2017-000877-35
Page 59 / 142

- For women of childbearing potential the method of contraception must be documented (as CM as applicable)
- Laboratory (haematology, biochemistry), serum pregnancy test (for women of childbearing potential)
- Pharmacogenomic blood sample
- Electrocardiogram, heart rate, blood pressure
- Eye examination
- Cognitive assessment (MoCA)
- Columbia-Suicide Severity Rating Scale (C-SSRS)
- Fatigue assessment (FSS)
- Assessment of sleepiness scales: ESS
- Other scales: HAM-D, BPRS+ and Berlin Questionnaire
- Determination of subject eligibility
- Recording of adverse events

### Baseline assessments (Day -7 to Day -2)

Baseline assessment will be performed after subjects have passed all the screening assessments and up to 1 week prior to the day of the 1st treatment administration (Day 1). The following procedures will be performed and documented during the Baseline period:

- Re-assessment of inclusion / exclusion criteria.
- Medical history and previous medication
- Laboratory (haematology, biochemistry), serum pregnancy test (for women of childbearing potential) if there is more than 14 days between screening and baseline.
- Maintenance of Wakefulness Test (MWT)
- Polysomnography
- Wrist-worn actigraphy (GENEActiv®) assessment 7 days continuously before the first dose on Day 1
- Recording of adverse events
- Recording of concomitant medication

Amendment 04, Final Version 1.0
Protocol No.: BB-2001-201b 07/Nov/2018
EudraCT No.: 2017-000877-35 Page 60 / 142

# Randomisation Visit 1 (Day -1)

- Re-assessment of inclusion / exclusion criteria.
- Urine dipstick for pregnancy assessment.
- Assessment of sleepiness scales: ESS, SCOPA-Sleep, PDSS-2
- Other scales: UPDRS Part III
- Wrist-worn actigraphy (GENEActiv®) assessment 7 days continuously before the first dose on Day 1
- Vital signs (including heart rate and blood pressure)
- Confirmation of subject eligibility
- Subjects will be randomised to their treatment assignments
- Study drug dispensing
- Recording of adverse events
- Recording of concomitant medication

# Treatment Visit 2 (Day 14 ±2)

This visit will be performed 2 weeks after the 1st treatment administration (Day 1). The following examinations/procedures will be performed:

- Vital signs (including heart rate and blood pressure)
- Assessment of sleepiness scales: ESS, SCOPA-Sleep, PDSS-2
- Other scales: UPDRS Part III, C-SSRS, HAM-D, BPRS+
- Dispensing of double blind study medication
- Drug return and accountability
- Recording of adverse events
- Recording of concomitant medication

# Treatment Visit 3 (Day 42 ±3)

This visit will be performed 6 weeks after the 1st treatment administration (Day 1). The following examinations/procedures will be performed:

- Physical examination
- Vital signs
- Laboratory (haematology, biochemistry), serum pregnancy test (for women of childbearing potential)
- Electrocardiogram, heart rate, blood pressure
- Assessment of sleepiness scales: ESS, SCOPA-Sleep, PDSS-2
- Maintenance of Wakefulness Test (MWT)

Protocol No.: BB-2001-201b EudraCT No.: 2017-000877-35 Amendment 04, Final Version 1.0 07/Nov/2018 Page 61 / 142

- Polysomnography
- Cognitive assessment (MoCA)
- Columbia-Suicide Severity Rating Scale (C-SSRS)
- Fatigue assessment (FSS)
- Other scales: UPDRS Part III, HAM-D and BPRS+
- Wrist-worn actigraphy assessment 7 days continuously **before** last dose (day 35 to day 42).
- Wrist-worn actigraphy device return
- Drug return and accountability
- Recording of adverse events
- Recording of concomitant medication
- Eye examination (should be performed after the last treatment on Day 42 and before the follow up safety call)

### **Early Termination**

In case of an early termination after 1st IMP administration and before treatment at visit 3 (day 42), the same procedures planned for the treatment at visit 3 (day 42) should be performed.

### Follow-up Period (+Day $28 \pm 2$ )

During the following up period the eye examination post dose on Day 42 will be conducted and a follow-up safety visit will be performed 28 days after the last IMP administration where the vital signs (including heart rate and blood pressure), C-SSRS, HAM-D, and BPRS+ will be assessed. The eye examination should be performed before the follow up visit. Additional unscheduled visits may be arranged as needed for the management of eye examination findings and / or adverse event findings.

## **Unscheduled Visit**

Unscheduled visits may be arranged following investigators' judgement for eye examination, or adverse event findings identified either at the end of study or during the follow-up period. The examinations/procedures may include:

- Physical examination
- Vital signs
- Laboratory (haematology, biochemistry), serum pregnancy test (for women of childbearing potential)
- Electrocardiogram, heart rate, blood pressure
- Other scales: C-SSRS, HAM-D and BPRS+
- Recording of adverse events

Amendment 04, Final Version 1.0
Protocol No.: BB-2001-201b
EudraCT No.: 2017-000877-35
Page 62 / 142

Recording of concomitant medication

### **Telephone Contacts**

Sites will maintain telephone contacts with subjects during the study as reminders for the study logistics, including the safety eye examination during follow-up.

# **Post-Study Care**

The study medication will not be available upon completion of the subject's participation in the study. The subject should be returned to the care of a physician and standard therapies as required.

### **8.4.3** Efficacy Variables

# 8.4.4 Primary Variables

The primary variable will be the mean absolute change of Bavisant treatment groups in the Epworth Sleepiness Scale (ESS) from baseline to the end of the 6-week treatment period, assessed as both the intragroup change compared to baseline and intergroup change compared to placebo.

# 8.4.5 Secondary Variables

Secondary variables will assess the efficacy on both the excessive daytime sleepiness and PD concomitant conditions:

Efficacy in Excessive Daytime Sleepiness (EDS):

- Mean absolute change in the Epworth Sleepiness Scale (ESS) from baseline to the end of the 2-week treatment period.
- ESS clinical response, defined as ESS absolute decrease from baseline of at least 3.0 points, after 2 and 6 weeks of treatment.
- ESS clinical response, defined as ESS  $\leq$  10 after 2 and 6 weeks of treatment.
- ESS clinical response, defined as either ESS  $\leq$  10 after 2 and 6 weeks of treatment or ESS absolute decrease from baseline of at least 3.0 points after 2 and 6 weeks of treatment.
- Mean relative change in the Epworth Sleepiness Scale (ESS) from baseline to the end of the 2-week and 6-week treatment periods (percentage of absolute decrease compared to baseline ESS).
- Mean absolute change in the Scales for Outcome in Parkinson's Disease Sleep (SCOPA-Sleep) from screening/baseline to the end of the 2-week and 6-week treatment period.
- Mean absolute change in the Parkinson's Disease Sleep Scale (PDSS-2) from screening/baseline to the end of the 2-week and 6-week treatment period.
- Mean absolute change in the Maintenance of Wakefulness Test (MWT) from baseline to the end of the 6-week treatment period.
- Mean absolute change in the polysomnography from baseline to the end of the 6-week treatment period.

Amendment 04, Final Version 1.0 Protocol No.: BB-2001-201b EudraCT No.: 2017-000877-35

Efficacy in Parkinson's disease (PD):

Mean absolute change in the MDS-UDPRS scale Part III (motor control) from screening/baseline to the end of the 2-week and 6-week treatment period.

07/Nov/2018

Page 63 / 142

- Mean absolute change in the depression HAM-D score from baseline to the end of the 2week and 6-week treatment period and safety follow-up.
- Mean absolute change in the Montreal Cognitive Assessment MoCA score from screening/baseline to the end of the 6-week treatment period.
- Mean absolute change in the Fatigue Severity Scale FSS score from screening/baseline to the end of the 6-week treatment period.

# **8.4.6** Exploratory Variables

The effect of Bavisant compared to placebo after the 6-week treatment period of free living activity will be assessed by means of wrist-worn actigraphy. For each set of continuous tri-axial accelerometry measurement, descriptive statistics of values at baseline, endpoint and change from baseline will be provided by treatment group.

Pharmacogenomic information will be assessed in order to identify genetic reasons why certain people respond differently to Bavisant, to find out more information about how Bavisant works, and to generate information needed for research, development, and regulatory approval of tests to predict response to Bavisant, and to identify variations in genes related to the biological target of Bavisant.

#### 8.4.7 **Safety Variables**

Safety variables will include:

- Incidence of Adverse Events (AEs) and Adverse Events of Special Interest (AESIs) like headache, nausea and insomnia
- Incidence of physical examination, vital signs and laboratory tests findings (haematology and biochemistry)
- Incidence of cardiovascular safety findings (blood pressure, heart rate, ECG including QT/QTc)
- Incidence of suicidal ideation (C-SSRS) findings from screening/baseline to the end of the 2-week and the 6-week treatment period and safety follow-up
- Incidence of positive psychotic symptoms (BPRS+) findings from screening/baseline to the end of the 2-week and the 6-week treatment period and safety follow-up
- Incidence of eye examination findings

Amendment 04, Final Version 1.0 07/Nov/2018 Page 64 / 142

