## 8.3. Prior and Concomitant Therapy

Any medication or therapy given in addition to the study medication is defined as concomitant medication/therapy (CM) and is to be thoroughly documented in the eCRF together with any previous medication administered within 4 weeks prior to the date of the informed consent signature. These may be prescribed by a physician or obtained by the subject over the counter. Concomitant medication is not provided by Sponsor.

At each study visit, subjects will be asked whether they have taken any medication other than the study medication (used from signing of informed consent through the end of the study), and all medication including vitamin supplements, over-the-counter medications, and oral herbal preparations, must be recorded in the eCRF.

To the extent possible, the dose of any CM required for chronic diseases should be kept as constant as possible throughout the study. Any changes in administration of any CM must be recorded by the investigator in the relevant eCRF page.

The following primary PD medications will be permitted at any time during the study if taken as stable medication for at least 4 weeks before screening. Any treatment / dose not described in this list should be checked with the medical monitor before deciding the subject randomisation:

- Dopaminergics
- L-dopa
- Monoamine oxidase inhibitors (MAOI)
- Short-acting antipsychotics if taken in the evening
- Catechol-O-methyl transferase (COMT) inhibitors
- Amantadine if not used as an alerting agent

Amendment 04, Final Version 1.0 07/Nov/2018 Page 46 / 142

At a minimum, the following medications will be prohibited at any time during the study (see exclusion criterion #8):

- Alerting agents, including r-modafinil, modafinil or methylphenidate
- Benzodiazepines
- Histamine active agents
- Hypnotics
- Cholinergics
- Skeletal muscle relaxants
- Clozapine
- Atomoxetine
- Amitriptyline
- Any other daytime medications which affect sleep

Subjects must be instructed not to take any other medication, including over-the-counter products, without consulting with the investigator first; who should contact the medical monitor for questions regarding episodic use.

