# 8.4.1.15.5 Brief Psychiatric Rating Scale Positive Subscale (BPRS+)

The Brief Psychiatric Rating Scale Positive Subscale (BPRS+) will be assessed at screening, visit 2 (day 14), visit 3 (day 42) or early termination, and follow-up visit (28 days after the last IMP administration).

The BPRS is an instrument originally developed to characterize psychopathology and to measure change in clinical psychopharmacology research. It permits the recording of severity of 18 (originally 16) distinct signs and symptoms of psychopathology such as hostility, suspiciousness, hallucination, and grandiosity, based on clinical interview of a patient. It is particularly useful in gauging the efficacy of treatment in patients who have moderate to severe psychoses, and based on the clinician's interview with the patient and observations of the patient's behaviour over the previous 2-3 days. The patient's family can also provide the behaviour report. The rater enters a number for each symptom construct that ranges from 1 (not present) to 7 (extremely severe).

Psychiatric symptoms, associated with PD itself and specifically in patients with Parkinson's psychosis, consist primarily of paranoid delusions, visual hallucinations and/or other sensory disturbances. Psychosis in PD most commonly manifests in visual hallucinations. Auditory hallucinations occur less commonly in PD psychosis (unlike hose seen in schizophrenia) and typically co-occur with visual hallucinations. Tactile, olfactory and gustatory hallucinations have also been reported in PD psychosis and also tend to co-occur with visual hallucinations, but less commonly than other forms of hallucinations. Delusions and is organized thinking are also seen in PD psychosis, although they are not as common as visual hallucinations.

While it is assumed that in this study adverse events known to occur with Bavisant will be directly assessed along with any sleep related effects, the Brief Psychiatric Rating Scale Positive Symptoms Subscale (BPRS+) would be appropriate to observe for psychiatric symptoms occurring in this study, with this population.

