The BPRS+ has been used in studies of major depressive disorders to observe for psychotic features occurring with drug treatment. It consist of 4 (Conceptual Disorganization, Suspiciousness, Hallucinatory Behaviour, and Unusual Thought Content) of the 18 domains of the full Brief Psychiatric Rating Scale and would cover those symptoms seen with Parkinson's psychosis. It could readily be taught to neurologists to perform in a reasonable amount of time during a study visit without becoming an undue burden on either the rater or the subject. The full BPRS with its 18 items would require extended time to teach and to perform without offering any clear additional benefit over the BPRS+ here.

Protocol No.: BB-2001-201b EudraCT No.: 2017-000877-35 Amendment 04, Final Version 1.0 07/Nov/2018 Page 57 / 142

Alternatives, such as the Positive and Negative Syndrome Scales (PANSS) have been discarded as being primarily used in schizophrenia which has psychotic features which differ from those seen with Parkinson's disease.

A BPRS+ sample questionnaire has been included in Appendix Error! Reference source not found.

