### 11.1.7 Safety Analyses

Adverse events, adverse events of special interest, serious adverse events, serious and related adverse events will be coded using the latest available MedDRA version and their corresponding incidences will be summarised as overall events, related events, and events by intensity. AEs will be summarised by MedDRA preferred term and system organ class (primary SOC). Summaries of AEs by preferred term and decreasing frequency and by maximum severity will also be prepared.

Physical examination changes, vital signs changes, laboratory tests changes, cardiovascular changes, ocular changes, suicidal ideation (C-SSRS) findings, and positive psychotic symptoms (BPRS+) findings will be described for the different treatment groups and assessed as either clinically or non-clinically significant findings.

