The BPRS consists of 4 symptom constructs ((#4, #11, #12, and #15) which ranges from 1 (not present) to 7 (extremely severe). 0 is entered if the item is not assessed. The total score is calculated as the sum of the scores of the 4 items. Incidence of patients with an increase and incidence of patients with a decrease from baseline in the BPRS+ total score will be described at the corresponding visit. Also the change from baseline will be descriptively analysed as a numerical data (see section 7 for further reference) for all patients, for patients with BPRS+ total score reduction and for patients with BPRS+ total score increase.

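### SAP 12.3 reports BPRS+ only as change in a four-item total, which is a poor measure of the protocol's endpoint, the incidence of positive psychotic symptom findings

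*Protocol*

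**What the plan says.** Protocol 6.2.2 and 8.4.7 set the safety endpoint: "Incidence of positive psychotic symptoms (BPRS+) findings from screening/baseline to the end of the 2-week" and 6-week treatment periods and the safety follow-up. Protocol 11.1.7 says how it is reported: the "findings will be described for the different treatment groups and assessed as either clinically or non-clinically significant findings". Neither section says what BPRS+ score makes a finding. Footnote 10 of the Schedule of Assessments (18.15) also refers to a positive BPRS+ finding and gives no score.

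Protocol 8.4.1.15.5 describes the subscale: "It consist of 4 (Conceptual Disorganization, Suspiciousness, Hallucinatory Behaviour, and Unusual Thought Content) of the 18 domains" of the full scale. It also says "Psychosis in PD most commonly manifests in visual hallucinations". In Appendix 18.10 each item runs from 1 (not present) through 2 (very mild) and 3 (mild) to 7.

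SAP 12.3 keeps the endpoint's title. Its content has two parts. One is a count: "Incidence of patients with an increase and incidence of patients with a decrease from baseline in the BPRS+ total score will be described", visit by visit. The other is a numerical summary of change in the total for all patients, for those with a reduction and for those with an increase. The SAP defines that total as follows: "The total score is calculated as the sum of the scores of the 4 items". On coding it says "0 is entered if the item is not assessed". SAP 14 states that the protocol's statistical content is unchanged.

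**The concern.** BPRS+ was added, with other assessments, following FDA safety requests (Reason for Substantial Amendment 03), because people with Parkinson's disease are at higher risk of psychosis. The question is how many subjects on each dose newly develop or worsen in a psychotic symptom. The direction of change in a sum of four different symptoms answers this only indirectly. The SAP treats the companion endpoint differently: for C-SSRS, section 12.2 defines a positive response and reports it at Visits 2 and 3 and at any time. BPRS+ has no such definition and no any-time summary. The protocol's clinical-significance classification is absent from 12.3, and SAP 14 does not mention its omission.

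**Working it through.** The documents give no rate, threshold or power for BPRS+, so there is no stated figure to reproduce. The scoring rule can be checked directly.

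**Inputs.** Four items (4, 11, 12, 15), each scored 1 to 7, with 0 for not assessed (SAP 12.3, Protocol 18.10). If all are assessed the total runs from 4×1 = 4 to 4×7 = 28. Completed subjects per arm: 50 (Protocol 11.2).

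**1. Offsetting between items.** Hallucinatory behaviour goes from 1 to 3 while suspiciousness goes from 3 to 1. The change in total is (+2) + (−2) = 0, so the subject is not counted as an increase.
- Let the other three items take scores 1 to 3 at both visits, and let a new hallucination score 2, 3 or 4. There are 27 × 27 × 3 = 2187 patterns, and 540 show no rise in total. This counts patterns and is not a probability.
- If every item is 1 at baseline and every item is assessed later, no pattern cancels.
- Offsetting between assessed items therefore needs a baseline item above 1. Protocol 8.2 has no BPRS+ exclusion, and 8.3 permits "Short-acting antipsychotics if taken in the evening", so such subjects are not ruled out.

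**2. The 0 code.** No rule keeps a 0 out of the sum. SAP 12.3 has no missing-item rule for BPRS+, although SAP 9.2 has one for several efficacy scales.
- Hidden increase: hallucinations go from 1 to 2 and another item from 1 to 0. The total stays at 4.
- False increase: one item is 0 at baseline and 1 later, the others stay at 1. The total goes from 3 to 4 with no symptom present.

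**3. No size threshold.** A total moving from 4 to 5 and one moving from 4 to 10 each count as one increase. To illustrate, assume all items are 1 at baseline and each is independently rated 1 point higher by chance with probability q. Then P(any increase with no true change) = 1 − (1 − q)^4. Suppose a dose also causes new hallucinations in 5% of subjects. For the total the probability becomes 1 − (1 − q)^4 × 0.95. For item 12 alone, counted at 2 or more, it moves from q to 1 − (1 − q) × 0.95. Both q and the 5% are assumptions.

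| q | Total: no effect | Total: with effect | Item 12 ≥ 2: no effect | Item 12 ≥ 2: with effect |
|---|---|---|---|---|
| 0.02 | 7.8% (3.9 of 50) | 12.4% (6.2) | 2.0% (1.0) | 6.9% (3.45) |
| 0.05 | 18.5% (9.3) | 22.6% (11.3) | 5.0% (2.5) | 9.75% (4.9) |
| 0.10 | 34.4% (17.2) | 37.7% (18.8) | 10.0% (5.0) | 14.5% (7.25) |

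The difference between arms is 50 × 0.05 × (1 − q)^4 = 2.31, 2.04 and 1.64 subjects for the total, and 50 × 0.05 × (1 − q) = 2.45, 2.38 and 2.25 for item 12. The item count gains only a little in the difference. Its main gain is a background about a quarter to under a third as large (1.0 against 3.9; 5.0 against 17.2), together with naming the symptom. A count at 3 or more would exclude 1-point changes from a baseline of 1, but would also miss real symptoms rated very mild.

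**The case against.** The case for the SAP has real force.

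- The protocol never defines a BPRS+ finding, so the SAP had no definition to depart from. The BPRS scoring instructions in Appendix 18.10 say to sum items and compare totals between evaluations (written for 18 items). This stands, and a total-score summary is legitimate. It does not explain the missing significance classification.
- Offsetting and the noise illustration rest on different baselines. At the floor assumed in the table nothing cancels unless an item is later coded 0, and any increase then means at least one item newly above 1. This stands. The documents give no frequency for offsetting.
- SAP 12.3 also summarises change for all patients, and SAP 7 includes the maximum. A rise from 1 to 6 on one item, others unchanged, would show as a change of +5. This stands, although the summary would not identify the item.
- Hallucinations recorded as adverse events appear by preferred term (Protocol 11.1.7). This stands in part. Protocol 9.1.2 keeps intermittent events of the underlying disease out of adverse event recording, so these tables are no full substitute for scheduled ratings.
- Protocol 8.4.1.15.5 names paranoid delusions as well as visual hallucinations, so hallucinations are not the only item of interest. This stands and supports reporting all four.
- Raters must be trained or certified (8.4.1.15.6), which may reduce rating noise. The table shells are a separate document (SAP 17) and may contain item rows; this cannot be checked.

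A reader might infer that the SAP discards the endpoint, or that the planned tables cannot reveal new hallucinations. The documents do not support either reading: the total carries information on the four symptoms, and the routes above recover part of it.

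**Conclusion.** The point holds as a limited gap that should be closed. The plan lacks a definition of a BPRS+ finding, and SAP 12.3 fills the space with any change in a sum. That sum can miss a new symptom in a subject with baseline symptoms, gives a 1-point rise the same weight as a large one, and can be distorted in either direction by a 0 code. The clearest departure from the protocol is the dropped clinical-significance classification, given that SAP 14 declares no changes.

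The scoring examples follow from the written rules. The share of unchanged subjects counted as increases (7.8% to 34.4%) depends entirely on the assumed noise rate of 2% to 10% per item, independence across items and a baseline of 1 on every item. Safety analysis is descriptive, so no test or error rate is affected. The loss is confined to the BPRS+ endpoint.

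**What to change.** Before unblinding, amend SAP 12.3 as follows.

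- For each of items 4, 11, 12 and 15, report by arm the number of subjects with new occurrence: 1 at baseline, then 2 or more post-dose, and separately 3 or more post-dose. These cut-offs are the scale's anchors for very mild and mild. The 2-or-more row still admits 1-point noise, which is why both are shown.
- For items already above 1 at baseline, report worsening by an amount stated in advance.
- Give these counts at Visit 2, Visit 3 or early termination, follow-up, and any post-dose visit.
- Add the split into clinically significant and not clinically significant required by Protocol 11.1.7, and state who makes that judgement and when.
- Treat 0 as missing, in the item counts and in the total.
- Keep the all-patient summary of change in the total. Dropping the summaries within the increase and reduction subsets is optional: their sign is fixed by selection, but they do describe the size of changes.

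If the significance split is not added, SAP 14 should list its omission as a change. The cost is SAP wording and one extra descriptive table with small counts. The item counts need only scores already collected; the documents do not say whether a significance judgement for BPRS+ is recorded, so that should be confirmed.
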